4.5 Return or Destruction of Unused Devices

Returned and/or unused devices are to be destroyed or returned to the Sponsor at the Sponsor's discretion. All devices must be accounted for in the inventory log. If devices are to be returned to the Sponsor, the Sponsor will provide shipping instructions at that time.

5 Study Objectives

5.1 Primary Objective

The Primary objective of the study is to assess the efficacy of the ITP FIRTECH for treating subjects suffering from mild to moderate acute low back pain.

5.2 Secondary Objectives

The Secondary objectives of this study are listed below:

- To assess the efficacy of ITP FIRTECH on the subject disability.
- To assess the efficacy of ITP FIRTECH on the degree of subject mobility.
- To assess the safety of ITP FIRTECH

5.3 Exploratory Objectives

Exploratory objectives for this study include:

- To assess the frequency and use of rescue medication
- To assess the subject evaluations of least, average, and worst pain

6 Study Design

6.1 Overview of Study Design

This is an, open label, randomized, proof-of-concept clinical trial; comparing the ITP FIRTECH with a no-patch control arm. The study will be performed in Medical Centers and an online e-diary will be used.

A total of 2 site visits and 1 phone contact are planned during a maximum of 6 days of study duration, as shown in *Figure 2*.

[figure not shown]

Figure 2. Study Schema

6.2 Anticipated Duration of the Clinical Investigation

The estimated study duration from first enrollment to last Subject visit is approximately 2 months. This study duration will require approximately 5 subjects to be enrolled per week at each site.

6.3 Evaluation Criteria / Efficacy and Safety

6.3.1 Primary Efficacy Clinical Endpoint

A Numerical Rating Scale^[3] (NRS) responder at Day 5 at the on-site evaluation (defined as $\geq 30\%$ decrease from baseline of the instantaneous pain^[4] and no rescue medication)

6.3.2 Secondary Efficacy Clinical Endpoint(s)

Key secondary endpoints

• Normalized Sum of Pain Intensity Difference (PID, which equals the instantaneous NRS change from baseline) over 5 days (SPID₀₋₅). The Sum of Pain Intensity Difference (SPID) is to be calculated by multiplying the PID score at each post dose time point by the duration (in hours) since the preceding time point. The Normalized Sum of Pain Intensity Difference (SPID₀₋₅) is to be calculated as the SPID₀₋₅ divided by the total duration time..

Normalized
$$SPID_{0-5} = \frac{\sum_{i=1}^{9} (T_i - T_{i-1}) * PID_i}{T_9 - T_0}$$

where $T_0 = 0$, T_i – actual time and PID_i – Pain Intensity Difference score at time T_i . Pain Intensity Difference, in turn, is defined as $PID_i = PI_i - PI_0$ where PI_0 – Pain Intensity at time T_0 .

- Roland-Morris Disability Questionnaire^[5] (RMDQ) score improvement (%) from baseline to Day 5. Details of the scoring of the Roland-Morris Disability Questionnaire are provided in Section 17.1.
- Mobility evaluation^[6,7]: change from baseline to Day 5. The mobility evaluations (Schober's Test or Fingertip to Floor Test) are described in Section 17.2.
- Time to reach acceptable pain. Time from randomization to the first report of acceptable pain; if that event never occurs, the tine will be censored at the final visit.

Other secondary endpoints

- Time to reach no pain (NRS = 0). Time from randomization to the first report of NRS=0; if that event never occurs, the time will be censored at the final visit.
- Time course of PID (see above) over time from baseline to Day 5 on-site evaluation
- Time course of Pain relief over time from baseline to Day 5 (VRS)
- Normalized Sum of Pain relief over 5 days (TOTPAR₀₋₅). Total pain relief (TOTPAR) is calculated by multiplying the pain relief score at each post-dose time point by the duration (in hours) since the preceding time point. The Normalized Sum of Pain Relief (TOTPAR₀₋₅) is to be calculated as the Total Pain Relief divided by the total duration time.

Normalized TOTPAR₀₋₅ =
$$\frac{\sum_{i=1}^{9} (T_i - T_{i-1}) * PAR_i}{T_9 - T_0},$$

where $T_0 = 0$, T_i – actual time and PAR_i – Pain Relief score at time T_i .

6.3.3 Exploratory Endpoints

- Frequency of use of rescue medication
- Description of "worst pain" evaluation
- Description of "least pain" evaluation
- Description of "average pain" evaluation

6.3.4 Safety Endpoints

Safety endpoints will include:

- Incidence of Adverse Events
- Incidence of Serious Adverse Events
- Incidence of Treatment Emergent Adverse Events

6.4 Study Population

Study populations are defined in Section 8.1.

6.4.1 Sample Size

The efficacy of the patch will be assessed compared with no-patch use. The primary endpoint is the occurrence of being a NRS-responder at Day 5 defined as \geq 30% decrease from baseline of the instantaneous pain and no rescue medication. The responder proportion in the "no-patch" arm is unknown, and a variety of proportions of responders are envisaged. The targeted treatment effect size is medium (Cohen's H ranging from 0.42 to 0.45). Ninety evaluable subjects per group (180 evaluable subjects in total) are needed to reach 80% power, as shown in the following table.

Alpha N per Group **Responder Rate** Cohen's H (2 sided) No Patch Patch 90 5% 10% 27% 0.449 90 5% 20% 39% 0.422 90 5% 30% 51% 0.432 90 5% 40% 61% 0.423 90 5% 50% 71% 0.433 90 0.422 5% 60% 80% Powers are calculated using East 6.4

Table 2. Power Calculations

Further assuming a dropout rate of 10%, the expected number of subjects to be randomized is a total of 200. Subjects will be randomized 1:1 to the treatment and no patch arms. The estimated number to be screened to achieve 200 randomized subjects is 260.

6.4.2 Subject Recruitment

Subjects will be recruited from the geographic areas served by the participating clinical sites. Subjects will be recruited from the individual practices of the participating clinicians.

6.4.3 Subject Screening

Subject screening will be conducted to ensure that subjects meet the study inclusion and exclusion criteria. Re-screening of subjects who have failed a previous screening will not be permitted. Documentation will be required to confirm the following:

• Subjects have not received non-pharmaceutical treatments such as physiotherapy, heat treatments or massage therapy within 12 hours prior to

enrollment.

- Subjects have not received any medications for pain within the last 24 hours (48 hours for diclofenae or corticosteroids) prior to enrollment..
- Subjects must not have received a spinal injection to treat back pain within 6 months prior to enrollment.
- Subjects must not have had surgery due to back pain or rehabilitation due to back pain within 12 months prior to enrollment.
- Female Subjects of childbearing potential are not pregnant or breastfeeding. A urine pregnancy test will be required to confirm.

6.4.4 Prior and Concomitant Therapy or Medications

6.4.4.1 Prior and Concomitant Therapies

Subjects must not have received any therapeutic patches or medications for pain within the last 24 hours (48 hours for diclofenac or corticosteroids) prior to enrollment. Subjects must not have received a spinal injection to treat back pain within 6 months prior to enrollment. Subjects must not have had surgery due to back pain or rehabilitation due to back pain within 12 months prior to enrollment. Subjects must not have received non-pharmaceutical treatments such as physiotherapy, heat treatments, massage therapy or acupuncture therapy within 12 hours prior to enrollment.

6.4.4.2 Prior and Concomitant Medications

Subjects will refrain from using analgesics and anti-inflammatory drugs except as described in Section 6.4.4.3 below during the course of their participation in this study.

6.4.4.3 Rescue Medications

During the study, subjects can be treated with up to 2 g of Paracetamol per day (rescue therapy) to be documented in the e-diary. Any other analgesics and anti-inflammatory drugs as well as any non-pharmaceutical therapy are prohibited during the study duration, if a subject needs to use one of these options, it has to be documented in the e-diary.

6.4.5 Inclusion Criteria

Subjects will be eligible to participate in the study if **all** of the following conditions exist:

- 1. Male or female subjects who are ≥ 18 years and < 65 years.
- 2. Subjects suffering from mild to moderate acute low back pain.

- Low back pain (lumbar back pain) is defined as pain in the back from the level of the lowest rib down to the gluteal fold.
 - Acute episode is defined as acute pain with less than 1 month duration.
- With intensity ≤ 6 on 0-10 Numerical Rating Scale (NRS).

6.4.6 Exclusion Criteria

Subjects will be excluded from participation in the study if any of the following conditions exist:

- 1. Subjects suffering from any neurological pathology which could be responsible of the pain.
- 2. Subjects suffering from leg pain irradiation.
- 3. Subjects suffering from chronic lumbar pain of any etiology.
- 4. Subjects with chronic arthrosis and neurological symptoms
- 5. Subjects experiencing recent significant trauma (i.e., injury related to a fall from a height or motor vehicle crash, or from a minor fall or heavy lifting in a subject with osteoporosis or possible osteoporosis),
- 6. Subjects with major or progressive motor or sensory deficit, new-onset bowel or bladder incontinence or urinary retention, loss of anal sphincter tone, saddle anesthesia, history of cancer metastatic to bone, and suspected spinal infection.
- 7. Subjects clinically diagnosed with anxiety and/or depression
- 8. Subjects using any medication for their pain within the last 48 hours within enrollment into the study
- 9. Subjects taking any systemic medication for their pain within the last 24 hours (48 hours for diclofenac or corticosteroids).
- 10. Subjects currently using recreational or illicit drugs or with a recent history of drug or alcohol abuse or dependence.
- 11. Subjects with any other medical condition that would interfere with efficacy and safety assessments based on investigator's judgment.
- 12. Subjects having received non-pharmaceutical Lower Back Pain treatment(physiotherapy, heat treatment or massage) within 12 hours prior enrollment
- 13. Subjects having received spinal injection back pain treatment within 6 months prior enrollment
- 14. Subjects having received surgery due to back pain or rehabilitation due to back pain in the last 12 months
- 15. Subjects with a known sensitivity to paracetamol
- 16. Known cutaneous hypersensitivity to plaster
- 17. Subjects participating in another clinical study within the past 30 days

- 18. Subjects who are pregnant or breastfeeding. Contraception is mandatory
- 19. Subjects having damaged, non-intact, or scarred skin in or near the point of patch application.
- 20. Subjects having a known skin sensitivity.
- 21. Subjects having impaired blood circulation.

6.4.7 Exit / Discontinuation Criteria

Subjects will exit the study if any of the following conditions exist:

- 1. Subject voluntarily withdraws from the study.
- 2. Subject death.
- 3. Subject is non-compliant with the protocol (as defined in Section 7.9)
- 4. Subject's well-being, in the opinion of the Investigator, would be compromised by study continuation.
- 5. Subject experiences an Adverse Event leading to voluntarily withdrawal and/or requiring withdrawal as per Investigator judgement.

6.5 Premature Termination or Suspension of the Study

This study may be prematurely terminated or suspended if there is sufficient reasonable cause. If the study is prematurely terminated or suspended, the Principal Investigator (PI) will promptly inform study participants, the Institutional Review Board (IRB), and the sponsor will provide the reason(s) for the termination or suspension. Study participants will be contacted, as applicable, and be informed of changes to the study visit schedule.

Circumstances that may warrant premature termination or suspension include, but are not limited to:

- Determination of unexpected, significant, or unacceptable risk or residual risk to participants (as described in the risk analysis performed according to ISO EN 14971).
- Insufficient compliance to protocol requirements
- Data that are not sufficiently complete and/or evaluable

The Sponsor must suspend/terminate the study within 5 working days of that determination.

7 Study Procedures

7.1 Informed Consent

All subjects for this study will be provided a consent form describing this study and providing sufficient information for subjects to make an informed decision about their participation in this study. The consent form will be submitted with the protocol for review and approval by the IRB for the study. The formal consent of a subject, using the IRB-approved consent form, must be obtained before that subject is submitted to any study procedure. This consent form must be signed by the subject or legally acceptable representative, and the investigator-designated research professional obtaining the consent. A blank copy of the IRB-approved form must be kept on-site and by the Investigator.

7.2 Vulnerable Populations

Recognized vulnerable populations will not be targeted for recruitment, however individual subjects within vulnerable populations may be enrolled. The Human Subject's Protections procedures employed in this protocol are sufficient to protect the rights and welfare of any subject within an eligible vulnerable population and no additional measures are necessary.

7.3 Randomization Scheme

Subjects will be randomized 1:1 to the investigational patch and no patch arms. Specific randomization procedures will be described in a separate randomization plan.

7.4 Blinding / Unblinding

This is an open label study, therefore there are no blinding / unblinding procedures.

7.5 Laboratory Testing Procedures

The only laboratory procedure utilized will be a urine pregnancy test administered to women of child-bearing potential.

7.6 Clinical Procedures

The study will be performed in Investigational Sites and an online e-diary will be used.

A total of 2 site visits and 1 phone contact are planned during a maximum of 5 days of treatment and 6 days of total study duration.

7.6.1 Day 1, Visit 1

Clinical procedures on Day 1, Visit 1 include the following:

- Verification of eligibility
- Informed Consent Signatures
- Local Physical Examination

- Collection of Vital Signs to include: Respiratory rate, Heart rate, Temperature, Blood Pressure
- Collection of Demographics to include: Age, Gender
- Collection of relevant medical history and concomitant medications
- On-line daily e-diary will be explained and activated
- Urine pregnancy testing (for women of childbearing potential only)
- Causes and/or circumstances triggering the acute back pain
- Baseline Subject symptom self-assessment
 - Pain Perception (NRS): Numerical Rating Scale^[3] for pain assessments at baseline and at defined time points: 0-10 NRS; '0' representing "no pain" and '10' representing "worst pain imaginable
 - Instantaneous: pain at the moment of the evaluation
 - Average pain in the previous 12 hours.
 - Worst pain in the previous 12 hours
 - Least pain in the previous 12 hours
 - o Roland-Morris Disability Questionnaire (RMDQ)^[5]
- Baseline mobility assessment (physician)
- Randomization:
 - O Arm A: ITP FIRTECH: Patch application according to the instruction for use in Section 17.3: The patch has to stay in position for 5 days. If the patch is taken-off or if it fell off during the study duration, the subject is invited to replace the patch at home following the instruction for use. Subject is allowed to take-off the patch at any time in case of severe skin itchiness, irritation, or skin reaction and in this case the subject has to contact the study center.
 - o Arm B: no-patch: Subjects will be informed that they will not be assigned a patch in this study.
- All subjects are informed that rescue mediation (paracetamol, up to 2 g per day), while not encouraged, is allowed if necessary.
- All subjects will be informed of the prohibited medications.
- If rescue medication is taken, the exact moment(s) and the dose(s) have to be indicated in the e-diary.
- An explanation will be provided on how to use e-diary at home and providing all necessary access credentials
- All subjects will be requested to avoid bed rest and will be recommended to continue with a normal daily life activity.
- Two extra patches will be provided to the subjects.
- Instruction will be provided on how to apply a patch at home, as per protocol Section 17.3.

7.6.2 Day 1 to Day 5, At Home

The following procedures will take place while subjects are at home:

- Completion of the e-diary in the morning (e.g. 8:00 [use 24 hr time format]) (this is not applicable at Day 1)
 - o Pain perception (using NRS)
 - Instantaneous: pain at the moment of the evaluation
 - Average pain in the previous 12 hours.
 - Worst pain in the previous 12 hours
 - Least pain in the previous 12 hours
 - o Pain relief (Using VRS) for the question "Do you feel pain relief?" 0= 'none', 1= 'slight', 2= 'moderate', 3= 'lots', 4= 'complete'.
 - o Is the Pain acceptable (binary, Yes/No)?
 - Need of rescue medication (time and dose)
- Completion of the diary in the evening (e.g. 20:00 [use 24 hr time format]) (this is not applicable at Day 5)
 - o Concomitant therapies, if any
 - Daily activities to include showers, physical activities, sporting activities, etc.
 - o Pain Perception (using NRS)
 - Instantaneous: pain at the moment of the evaluation
 - Average pain in the previous 12 hours.
 - Worst pain in the previous 12 hours
 - Least pain in the previous 12 hours
 - o Pain relief (Using VRS)
 - o Is the Pain acceptable?
 - Need of rescue medication (time and dose)
 - Adverse events
 - Need of patch removal and application of a new patch according to instructions for use (Section 17.3) and recording of reason.

7.6.3 Day 5, Visit 2 Patch Removal / End of Treatment

Clinical procedures on Day 5, Visit 2 (Investigational Site) include the following:

- Completion of the e-diary on site
 - o Pain perception (using NRS)
 - Instantaneous: pain at the moment of the evaluation
 - Average pain in the previous 12 hours.
 - Worst pain in the previous 12 hours
 - Least pain in the previous 12 hours
 - Pain relief (Using VRS)

- o Is the Pain acceptable?
- o Need of rescue medication (time and dose)
- o Adverse Events
- o Concomitant therapies if any
- E-Diary verification
- Arm A Subjects: Patch is removed.
 - o Collection of all used and unused patches.
- Arm B Subjects: subjects are informed about the end of the evaluation period
- Local physical examination, including at patch localization (only for Arm A subjects)
- Vital signs
- Roland-Morris Disability Questionnaire (RMDQ)^[5]
- Mobility assessment (physician)

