7.8 Study Timetable / Schedule of Events

Table 3. Schedule of Events

Visits	V1	At	V2	Phone	Unsch	Notes
		Home		Call		
Days	D1	D1 to	D5	D6		
		D5				
Eligibility verification	✓					
Informed Consent	✓					
Demographics /	✓					
Medical History						
Physical Exam	✓		✓		✓	
Vital Signs	✓				✓	

Visits	V1	At	V2	Phone	Unsch	Notes
		Home		Call		
Days	D1	D1 to D5	D5	D6		
Urine Pregnancy Test	√					For women of child-bearing potential only
E-diary Activation	✓					
Randomization	✓					
E-diary Completion	✓	√ *	√ **			*2 times per day at the same times **On-site evaluations
Pain perception	✓	✓	✓			
Pain-relief evaluation		✓	✓			
Pain acceptable perception		~	√			
Rescue Medication Needed		V	√			
Roland-Morris Disability Questionnaire	√		√			
Mobility assessment	√		√			Schober's Test or Fingertip- to-floor test
Adverse Event assessment	√	~	√	√	√	
Patch application / removal	✓		✓		✓	Patch(es) has(have) to be used for 5 days. If the patch is taken-off for a safety reason, the subject has to contact the study center. If the patch falls off, the subject has to replace it as soon as possible. The subject will complete the diary card, informing about the patch replacement, the reason of change, and the time spent with no patch.
Concomitant therapies	✓	✓	✓	✓	✓	
e-diary review			√		√	

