8.3.1.5 Adjustments for Multiple Testing

Adjustment for multiple testing will be done as follows:

- The multiplicity of key secondary endpoints will be handled using a False Discovery Rate (FDR) approach. Nominal p-values will also be displayed.
- For the other secondary endpoints and the exploratory endpoints, p-values will be provided for descriptive purpose only.
- The number of adverse events defined as other secondary endpoint will be analyzed only with descriptive statistics (no p-value will be provided).

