9.4.1 Adverse Events

All observed or volunteered adverse effects and abnormal test findings, regardless of treatment group, if applicable, or suspected causal relationship to the investigational device or, if applicable, other study treatment or diagnostic product(s) will be recorded in the subjects' case histories. For all adverse effects, sufficient information will be pursued and/or obtained so as to permit:

- 1) an adequate determination of the outcome of the effect (i.e., whether the effect should be classified as a serious adverse effect) and;
- 2) an assessment of the casual relationship between the adverse effect and the investigational device or, if applicable, the other study treatment or diagnostic product(s).

Adverse effects or abnormal test findings felt to be associated with the investigational device or, if applicable, other study treatment or diagnostic product(s) will be followed until the effect (or its sequelae) or the abnormal test finding resolves or stabilizes at an acceptable level.

Adverse Events that do not qualify as Serious Adverse Events, or as Unanticipated Adverse Device Effects will be reported to the Sponsor at designate interval determined by the Sponsor.

Adverse Events that do not qualify as Serious Adverse Events, or as Unanticipated Adverse Device Effects will be reported the IRB with the continuing review progress report.

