5.1.8.1 Adverse Events (AE)

All verbatim AE terms will be coded using the MedDRA (version 24.1), listed and summarized by SOC and PT for Safety Population by treatment group and overall.

Treatment-Emergent Adverse Events (TEAEs) will be defined as AEs not present prior to the first patch application (FIRTECH Patch) or randomization (No Patch), or AEs present before that worsened after the first patch application (FIRTECH Patch) or randomization (No Patch). If a partially missing date of onset allows the possibility that an AE may be a TEAE it will be presumed to be a TEAE. Unanticipated Adverse Device Effect (UADE) will be defined as any serious TEAE related to the study device.

TEAEs will be analysed by treatment group and overall. UAED will be analysed only for FIRTECH Patch treatment group.

AEs will be summarized by treatment group and overall by the number and percentage of subjects who experienced at least one AE of any of the following types: any AE, any TEAE, any device-related

CONFIDENTIAL Page 24 of 30

Study No LPS16453 Date: DEC 12, 2022

Private and Confidential

TEAE, any serious TEAEs, any UADE, any SAE leading to death, any TEAE leading to study discontinuation, any serious TEAEs leading to study discontinuation.

TEAEs will be summarized by the highest relationship to study device (Related or Not Related) and maximum severity (Mild, Moderate, Severe). If the relationship of AE or TEAE to the study device is unknown, then the event will be classified as Related.

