5.1.8.3 Physical Examination

The physical examination will be listed and summarized for the Safety population by treatment group and overall by the number and percentage of subjects with abnormalities of the spine (lumbar lordosis, scoliosis, kyphosis, other), asymmetry and integumentary findings on the lower back (mole, scar, birth mark, discolouration, other) by visit (Baseline Visit 1 and Day 5 Visit 2).

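### Protocol 7.6.3 leaves open whether the no-patch arm has the Visit 2 local examination, although the SAP tabulates lower-back skin findings at that visit by arm

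*Protocol*

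**What the plan says.** **Visit 1.** Protocol 7.6.1 lists "Local Physical Examination" for every subject, ahead of randomization and with no arm limit.

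**Visit 2.** Protocol 7.6.3 lists "Local physical examination, including at patch localization (only for Arm A subjects".

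**Schedules.** The "Physical Exam" row of Protocol Table 3 is ticked at V1, V2 and unscheduled visits with no arm restriction. SAP Table 1 repeats this.

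**Skin harm.** Protocol 9.2.1 ties the assessment of skin reactions to the moment the patch comes off. Section 9.3 names minor skin irritation at the application site as the anticipated adverse event and says its frequency is not known.

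**Recording.** Protocol 9.4.1 covers "All observed or volunteered adverse effects and abnormal test findings, regardless of treatment group".

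**Analysis.** Under SAP 5.1.8.3 the physical examination is "listed and summarized for the Safety population by treatment group and overall", including "integumentary findings on the lower back (mole, scar, birth mark, discolouration, other) by visit (Baseline Visit 1 and Day 5 Visit 2" (Table 14.3.5.2). SAP 5.1.8.1 adds: "AEs will be summarized by treatment group and overall by the number and percentage of subjects who experienced at least one AE". Protocol 8.3.1.5 says that the number of adverse events "will be analyzed only with descriptive statistics (no p-value will be provided".

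**The concern.** The SAP sets lower-back skin findings at Visit 2 side by side for the two arms, but the protocol sentence that generates those data carries a restriction to Arm A. If investigators look at the skin more closely in the patch arm, or only there, a finding that would have appeared anyway is recorded in Arm A and may go unrecorded in Arm B. The difference between the columns then mixes device effect with extra looking.

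This matters because safety is a secondary objective and the anticipated harm is a skin reaction of unknown frequency. The no-patch arm is the only source within the trial for the background rate of such findings over five days. Adhesive reactions cannot occur in Arm B, which is why Arm B is useful for separating background from device effect.

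There is also a denominator problem if sites read the sentence differently. SAP 3.2 bases percentages on non-missing values, so the No Patch percentage could come only from the sites that happened to examine Arm B.

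**Working it through.** The plan states no figure on this point, so there is none to reproduce. The check is a comparison of texts, followed by a scale illustration.

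**Step 1: which reading do the other texts support?**

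- *Broad reading* (the bracket governs the whole item, so Arm B has no local examination at Visit 2). This conflicts with the unrestricted V2 tick in Protocol Table 3 and SAP Table 1, and with SAP 5.1.8.3, which expects Visit 2 data in both groups.
- *Narrow reading* (the bracket governs only the patch-site part). This agrees with both schedules and with SAP 5.1.8.3. It also fits the style of 7.6.3, where the other single-arm items open with the arm's name as a label and this one does not.

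The narrow reading is therefore better supported, but the schedule does not settle the matter. As the tables read in the text available, both leave vital signs unticked at V2, while 7.6.3 lists them there and SAP 5.1.8.2 summarises them at Day 5 Visit 2. A site could reasonably follow the procedure list instead of the table. SAP 5.1.11, which lists changes from the protocol, does not mention the examination.

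**Step 2: what does Arm B receive under each reading?**

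- *Broad:* no local examination at Visit 2. With 200 randomised 1:1, that is 200 / 2 = 100 subjects whose column in Table 14.3.5.2 would lack Visit 2 data.
- *Narrow:* a local examination, but no directed inspection of the skin area that corresponds to the patch site. The protocol does not define the content of the local examination; only the SAP's list of summarised findings shows that lower-back skin is meant to be covered.

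**Step 3: scale, under assumptions.** Let r be a true rate of new lower-back skin findings that is equal in both arms. Suppose all Arm A findings are recorded and a share s of Arm B findings is recorded. Then

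spurious difference = r × (1 − s).

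Neither r nor s is in the documents. For assumed values:

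| r | s = 0 | s = 0.5 | s = 1 |
|---|---|---|---|
| 2% | 2 points | 1 point | 0 |
| 5% | 5 points | 2.5 points | 0 |
| 10% | 10 points | 5 points | 0 |

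The column s = 0 needs the broad reading and nothing reported or noticed in Arm B by any other route. The column s = 1 is what follows if Arm B has the same examination. The table shows how the artefact behaves and is not an estimate for this trial.

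**The case against.** The strongest reply is that the bracket follows directly on the mention of the patch site, which Arm B does not have, so it most naturally limits that phrase alone. Both arms then have the local examination. SAP 5.1.8.3 shows that it covers skin of the lower back, the region where Protocol 17.3 places the patch. Inspecting skin under a patch just removed is device-specific follow-up and needs no counterpart.

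Beyond the examination, adverse events are collected in both arms by evening diary, at Visit 2 and by the Day 6 call, and are recorded regardless of group. Treatment-emergent events must be new or worse than before treatment, and everyone is examined at Visit 1. The safety tables carry no test. Moles, scars and birth marks hardly change in five days, and exclusion criterion 19 already removes damaged or scarred skin near the site. Any leftover effect would overstate patch harm, not conceal it.

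Much of this stands. It shows that the narrow reading is more likely, that the exposed part is small (mainly discolouration, other new findings and events noticed at the examination), and that its direction is against the device. It does not remove the ambiguity. Collecting adverse events in both arms does not equalise observed findings if the skin is looked at differently, and where there are no p-values the raw counts are the safety evidence.

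A reader might infer that Arm B is not examined at Visit 2, or that skin findings are sought in one arm only. The documents do not support either statement: each needs the broad reading, which three other places contradict, and nothing shows Arm B data to be missing.

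**Conclusion.** The point holds as an ambiguity with a possible consequence. The scope of the Arm A restriction in 7.6.3 is unclear. Read broadly, it contradicts Protocol Table 3, SAP Table 1 and SAP 5.1.8.3. Read narrowly, as those places favour, it still prescribes a directed inspection of the application area in one arm only. The comparison of lower-back skin findings and examination-detected adverse events **may** therefore reflect unequal ascertainment.

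It would go too far to call the harm comparison biased. The size cannot be given from the documents, because it depends on a background rate and a detection share that they do not state. It lies between zero, if both arms are examined alike, and the full background rate, if nothing is recorded in Arm B. This is a low-cost clarification and does not challenge the trial's safety conclusions.

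**What to change.** **Protocol 7.6.3.** Remove the arm restriction and require the same Visit 2 local examination of the lower back in both arms. It should cover the skin of the patch application area in Arm A and of the corresponding area in Arm B, and be recorded on the same CRF page with the same list of findings. This brings Visit 2 into line with Visit 1, Table 3 and SAP 5.1.8.3.

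**Visits already held.** SAP 3.4 relies on a memo of 22 November 2022 about Visit 2 records, so some of these visits had taken place by then. For these, first count the Arm B examination records at Visit 2, by site. If Arm B was examined, keep Table 14.3.5.2 as planned. Only if it is confirmed that Arm B was not examined should the SAP show the Visit 2 skin findings for the patch arm alone and flag treatment-emergent events first detected at that examination, so that the between-arm summary can also be given without them. Taking this step without confirmation could discard valid planned data.

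**Cost.** One line of protocol wording and about a minute of skin inspection per Arm B subject, at a visit they already attend for the physician's mobility assessment. The conditional step needs SAP wording and one adverse-event flag.
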